***Significance***

Given the large number of military personnel returning from combat operations in Iraq or Afghanistan with reported or suspected head injuries (Hoge et al., 2008), the outcome of the present study could have significant impact on the delivery of health care to returning military veterans. Other than cognitive-behavioral therapies and avoidance of re-injury, there are few alternative treatments for patients suffering from post-concussive symptoms secondary to a mild traumatic brain injury. Alternative approaches to treatment, or adjunctive approaches that can be used to augment ongoing treatments, are clearly needed. Because sleep disruption is one of the primary complaints of individuals following mTBI, and sleep is critical to neurogenesis and neural plasticity, sleep enhancement seems to be an ideal candidate for direct intervention. If the sleep problems can be improved, it is more likely that emotional difficulties will be reduced, ongoing treatments will be enhanced, and brain functioning can be restored to the fullest extent possible. Furthermore, non-pharmacologic interventions are generally preferable and more cost effective than reliance upon prescription medications for sleep problems. Therefore, it is hypothesized that by using light therapy to entrain the circadian sleep-wake cycle, we may improve sleep in a sample of individuals with a recent history of concussion, and thereby increase the likelihood that they will recover more quickly, benefit more extensively from other forms of therapy, and build emotional and cognitive resilience. If effective, the proposed approach could be used in isolation or as an adjunct to ongoing therapy to reduce the impact of mTBI and post-concussive symptoms, thereby facilitating a more rapid recovery. Even if the proposed light therapy fails to prove effective at improving sleep or symptom profiles, the obtained cognitive and neuroimaging data, neurocognitive testing, and actigraphy data will prove

**FORM: Application for Human Research**

NUMBER	FORM DATE	PAGE
F200	02/2014	10 of 39

invaluable in developing further insights into the relationship between mTBI, sleep, and brain function.

## 2) Lay Summary (approximately 400 words)

### **Main Study Arm:**

[name] and colleagues are conducting a research study funded by the Department of Defense to understand the effectiveness of a six-week course of light exposure on cognitive functioning, mood, activity, and sleep in people that have suffered a mild traumatic brain injury (mTBI) or “concussion.” This study will consist of four visits to the University of Arizona.

During the course of the study, participants will complete two cognitive testing sessions and magnetic resonance imaging (MRI) scans (1 hour each), which will occur 6 weeks apart. During the intervening 6-week period, participants will use a commercially available light device to provide 30-minutes of light exposure each morning. During the two testing and MRI scan sessions, participants will undergo a series of tests of attention, concentration, memory, and other cognitive abilities, and will complete clinical measures to assess mood and post-concussion symptom severity. Daily activity and sleep patterns during the entire 13-week period will also be monitored using self-report diaries, questionnaires, and a wrist worn activity monitor. This monitoring will continue for an additional 6 weeks after termination of the light exposure for subjects who elect to participate in this optional research.

In this study, we will use functional and structural brain imaging techniques such as functional magnetic resonance imaging (fMRI) and diffusion tensor imaging (DTI) to evaluate brain function and brain structure before and after the 6-week light exposure period. Identifying and mapping the brain systems before and after light exposure may help researchers develop further insights into the relationship between concussion, light exposure, sleep, and brain function.

Those deemed eligible to take part in this study will have experienced a mild traumatic brain injury (mTBI) or concussion during the past 18 months, but no sooner than four weeks prior to the screening. Approximately 40 individuals between the ages of 18 and 50 will participate in this study in order to obtain a final dataset of 30 due to attrition.

### **Healthy Control (HC)/Effect Localization Arm:**

This study will also have a healthy control (HC)/effect localization arm. We will enroll 50 healthy individuals ages 18 to 50 for this arm of the study. A simple computer randomization will be performed that assigns slots before the study begins. This block randomization will ensure essentially equal numbers of males and females.

These subjects will perform very similar activities as subjects for the main arm of the study, albeit, pared down as it is a streamlined, basic form of the main study arm. Their participation is expected to last one day over two visits and no more than approximately 5.5 hours.

During their initial visit, subjects will be asked to complete a single cognitive testing session and magnetic resonance imaging (MRI) scan. Prior to the scan, subjects will wear an EKG (electrocardiogram) device for the duration of the visit, save for the MRI scan. Subjects will complete study assessments (DOSQ, MEQ, PANAS, BDI-II, WASI, CVLT, SWLS) and then will be asked to sit in a room for 60 minutes of either 30 minutes of amber placebo light exposure followed by exposure to a blue wavelength light device (goLITE BLU) or an amber placebo/sham light device in

**FORM: Application for Human Research**

NUMBER	FORM DATE	PAGE
F200	02/2014	11 of 39

the same room for the full 60 minutes. During the 30 minute wash out and 30 minute light exposure periods, subjects will be asked to sit quietly for 10 minutes and fixate on a large cross opposite them in order to help get clean EEG data. During this time, their EEG (electroencephalography) will be recorded via leads attached to the subject's scalp to help measure brain activity. It must be noted that because subjects will see the color of light they will be exposed to, it is impossible to blind subjects to the condition. Hopefully, subjects will not be to knowledgeable about the effects of various wavelengths of light. Following this, participants will get into the fMRI scanner and will undergo a series of tests of attention, concentration, memory, and other cognitive abilities (CVLT II, MSIT, N-Back, BMAT, Anticipation Task), and will complete clinical measures to assess mood. Subjects will have their heart rate monitored via EKG during baseline and post treatment visits only. Subjects will complete several post-scan tests and questionnaires including the PANAS to conclude their participation. Over the course of the initial visit, subjects will also have 3 saliva collections to measure their melatonin levels. Before concluding their initial visit, subjects will be given and instructed in the use of an Actiwatch device to wear until their follow-up visit the same day.

Subjects will be asked to return for a follow-up visit at approximately 8:30pm the same day to collect a fourth and final melatonin sample as well as return the Actiwatch.

In this study, we will use functional and structural brain imaging techniques such as functional magnetic resonance imaging (fMRI) and diffusion tensor imaging (DTI) to evaluate brain function and brain structure. Identifying and mapping the brain systems before and after light exposure may help researchers develop further insights into the relationship between concussion, light exposure, sleep, and brain function and will provide brain targets for study in the analysis of the Main Study Arm.

Please note that all cognitive testing, questionnaires, and MRI/fMRI scanning for this healthy control arm are akin to the main arm of this study.

### 3) Setting of the Human Research

The main study arm requires three visits including an initial assessment and two testing/scanning sessions separated by six weeks of daily light exposure treatment at home. The healthy control or effect localization arm requires one day and two visits cumulatively lasting approximately 5.5 hours.

For the initial assessment and the baseline testing session, subjects will be seen at the Lab of [name] in the University of Arizona Department of Psychiatry. [name] lab in Suite 7304 consists of a lounge, two sleep lab rooms, and a testing room. There, subjects will complete personality assessments, a comprehensive cognitive assessment battery, and several tests of motor functioning.

Magnetic Resonance Imaging (MRI) Procedures: The data collection will occur at the research-dedicated University of Arizona scanner facility that houses a new 3 Tesla magnet (see Equipment for description). For functional neuroimaging, audio and visual stimulus presentation equipment is available through the Resonance Technologies headphone/goggle system or high-definition MRI-compatible LCD-display (viewed through a mirror in the head cage). An fMRI compatible EEG system including caps, cabling, and pre-amplifier is integrated with this space (see Equipment for description). Scanner data are transferred securely to a RAID storage system for subsequent transfer to PI laboratories. Offline analysis will take place in the Laboratory of PI [name].

**FORM:** Application for Human Research

NUMBER	FORM DATE	PAGE
F200	02/2014	12 of 39

In January 2013, the University of Arizona purchased a Siemens Magnetom TIM Skyra 3T that is capable of high-resolution imaging capabilities. This whole-body 3.0T device will be configured with 48 receiver channels and up to 204 integrated coil elements. It is capable of integrated parallel acquisition techniques and provides higher signal to noise in the parallel imaging mode than its predecessor, the Trio. The maximum acceleration factor using parallel imaging is 16 using either mSENSE or GRAPPA, and 3D scanning can be accelerated in two directions (maximum acceleration factor of 4 in second direction). The gradients of the Skyra have a maximum amplitude of 45 mT/m and a maximum slew rate of 200 T Tm^-1s, yielding a minimum rise time of 225µs. The vector gradient performance (vector summation of all three gradient axes) results in a maximum effective amplitude of 78 mT/m and a maximal effective slew rate of 346 Tm^-1s. All three gradient coils are force-compensated to reduce vibration and deliver superior eddy current performance. The water cooled gradient amplifier has a maximum amplitude potential of 2,250 volts and a maximum current output of 750 amps. The instrument has a minimum slice thickness (in two dimensions) of 0.1 mm and a minimum partition thickness (in three dimensions) of 0.05 mm. The instrument produces high sensitivity, with main field, or B0, homogeneity of 1.4 ppm VRMS for a 40 cm diameter spherical volume. Single shot EPI sequences for measuring diffusion-weighted data sets with up to 256 directions of diffusion weighting are also a part of this instrument's capability. It provides diffusion tensor imaging and parametric maps derived from fractional anisotropy calculated in real time, automatically. Additional sequence options include Arterial Spin Labeling, and susceptibility weighted imaging (SWI) with both fully supported with parametric and phase map reconstructions.

All structural and functional MRI studies will be conducted in concert with University of Arizona Medical Imaging.

MRI will be conducted at the Translational Bioimaging Resource (TBIR), housed in the basement of the Biosciences Research Labs (BSRL) building. The 12,000 sq. ft. TBIR serves as a university-wide resource for pre-clinical biomedical imaging. BSRL is equipped with waiting areas, dressing rooms, and storage lockers for participant comfort and convenience. The elevator down to the TBIR is limited access, operable only by staff with an authorized CatCard, who will escort subjects to the scanner area. Designated MRI participant parking is located directly across the street from the BSRL building. The TBIR houses a 3 Tesla Siemens Skyra VE11 capable of supporting a wide range of research, including arthritis, traumatic brain injury, PTSD, cancer treatment efficacy, depression, kidney transplant viability, CPR, Alzheimer's, complex grief, and healthy aging. Subjects in this study will be studied in a scanner that has a field strength of 3 Tesla. This field strength has been approved by the FDA for routine clinical use. The three instruments are maintained by GE service engineers and currently meet or exceed manufacturer's specifications on performance. For functional neuroimaging, audio and visual stimulus presentation equipment is available through the Resonance Technologies headphone/goggle system.

A research area, located immediately adjacent to the 3.0 Tesla scanner, is equipped with 3 PC/Linux workstations and an sgi O2 for data transfer and storage, image processing, and data manipulation. All workstations are networked through a central hub and are protected against external tampering using firewalls within the UAMC computer network.

**FORM: Application for Human Research**

NUMBER	FORM DATE	PAGE
F200	02/2014	13 of 39

Functional MRI is mostly done in MR3, a General Electric 3.0T HD Signa Excite scanner. It is equipped with Optimized ACGD Gradients (40mT/m, 150 mT/m/ms slew rate running 12x software). It is a 55cm diameter long bore magnet. This instrument is equipped with a head coil, 8 channel HR brain array, a phased array neurovascular coil, 8 channel phased array spine coil, extremity coils (knee and wrist) and a torso coil. MR3 has multinuclear spectroscopy capability and high order shims.

#### **4) Resources available to conduct the Human Research**

[name] effort is 100% devoted to research; he does not have clinical or teaching time mandated as part of his FTE. He funds at a minimum two full-time research technicians (Research Assistants) and one full-time postdoctoral research associate.

The Department of Psychiatry has staff devoted to research administration, including an upper level administrator and a regulatory coordinator. All have experience with IRB/regulatory matters and grants administration. Business office staff is knowledgeable in grants finance and accounting, and federal work-study students devoted to research are available for data entry and other administrative support.

[name] Deprivation Lab includes computing equipment such as backup drives and external hard drives, backup surge protectors, intercom system, neuroimaging workstations with 6 TB minimum storage each; Actiwatch sleep monitors watches, docks, and software analysis programs; Coulbourne Fear Conditioning Suite, FaceRead + Observer XT System, sleep profiler ambulatory EEG monitoring systems, and other software including EPrime, MatLab, SPSS, and Adobe Captivate.

The Department of Psychiatry provides personal computer resources for word processing, email transmission, internet access, and simple statistical analysis for staff, in addition to laser printers, fax machines, scanners and photocopy machines. In addition to these resources, the University of Arizona maintains full computer and data analytic processing components available to all university faculty on a fiber-optic network system, with automatic daily backup available on a secure server. There is full time computer support in the Department of Psychiatry for these resources.

University of Arizona Medical Center (UAMC) is a private, non-profit 487-bed acute-care hospital in Tucson, Arizona. UAMC has two units: University Campus and South Campus. The University of Arizona affiliated medical services include: University Medical Center, University Physicians Healthcare, and the College of Medicine. UAMC is part of Arizona Health Sciences Center (AHSC) campus, including the Colleges of Medicine, Nursing, Pharmacy and Public Health. Additionally, UAMC is an American Nurses Credentialing Center (ANCC) Magnet Hospital.

The Clinical and Translational Sciences Center (CaTS) storage area contains protected access freezers where all saliva samples will be stored and protected. The University of Arizona Cancer Center (UACC) lab room 4916 will serve as the site for melatonin sample analysis.

All study personnel will have up to date CITI training and study protocol training from the PI or PI designee.

#### **5) Study Population**

##### **Main Study Arm:**

**FORM: Application for Human Research**

NUMBER	FORM DATE	PAGE
F200	02/2014	14 of 39

Forty (40) individuals between the ages of 18 and 50 with a documented history of a “concussion” or mTBI in the preceding 18 months but no sooner than 4 weeks prior to the screening will be recruited to participate in the main study arm. It is anticipated that approximately 6 participants (i.e., 17%) will withdraw early or fail to comply with procedures. Thus, a total of 40 participants will be run to achieve a total sample size of 30 complete datasets. The occurrence of a concussion or mTBI must be documented by a medical/objective professional (e.g., sports trainer, coach, physician, nurse, etc.) report. In addition, at least half of the participants recruited for each condition will be required to have complaints consistent with sleep onset insomnia (i.e., trouble falling asleep) as measured by Insomnia Severity Index (ISI) or delayed sleep phase disorder (i.e., not feeling sleepy at bedtime and/or not able to fall asleep until much later than bedtime). Participants with a lifetime history of head injury leading to loss of consciousness greater than 30 minutes will be excluded. Other exclusion criteria will include any current medical condition that would be contraindicated for scanning, other known neuropathology (e.g., tumor, neurodegenerative disease, normal pressure hydrocephalus, etc.), abnormal visual acuity that is not corrected by contact lenses, metal within the body, or time since injury exceeding 18 months.

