**FORM: Application for Human Research**

NUMBER	FORM DATE	PAGE
F200	02/2014	9 of 39

laboratory and provide excellent resolution for evaluating functional changes within the target regions of the anterior cingulate gyrus, hippocampus, and prefrontal cortex. Furthermore, the proposed project will directly assess sleep functioning using actigraphy and correlate these changes in sleep with pre-to post-treatment changes in neurocognitive performance and symptom presentation, as well as functional activity changes.

Briefly, individuals who have experienced a mTBI, with or without loss of consciousness, as verified by a medical report, and who complain of sleep disturbance, will undergo an initial psychological assessment, and will be then fitted with an actigraph to wear for the duration of the study in order to measure baseline sleep as well as any changes in sleep patterns. Individuals will then return to complete two comprehensive neurobehavioral assessment and neuroimaging sessions (functional MRI, structural MRI/diffusion tensor imaging; DTI) separated by 6 weeks. During the intervening 6 weeks, participants will be randomly assigned to receive 30 minutes of morning blue light therapy (MBLT) or a sham placebo amber light treatment (SPLT) daily. Sleep quality and quantity will be measured via continuous wrist actigraphy monitors and self-report inventories.

For interested subjects participating in the last phase of recruitment, we will continue collecting wrist actigraphy and self-report data for an additional 6 weeks after completion of the baseline period and light therapy as an optional part of the study. It is hypothesized that MBLT will improve sleep quality and quantity relative to SPLT, and these improvements will be associated with changes in brain function, brain structure, and reduced post-concussion symptom severity at follow-up assessment.

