**Inclusion criteria:**

- Age range between 18 and 50.
- The primary language of the subjects must be English.
- Subjects have experienced a “concussion” or mTBI within the preceding 18 months, but no sooner than 4 weeks prior to their screening. The occurrence of a concussion or mTBI must be documented by a medical report or other professional witness documentation.
- If documented, Glasgow Coma Scale in the range of 13-15 following the injury.
- At least half of subjects must have evidence of sleep onset insomnia or delayed sleep phase disorder.

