### Telephone Screening

All potential volunteers will initially be screened via telephone interview with a trained research technician. Screening will include basic information about the study and its requirements. Potential volunteers will be asked a series of screening questions to determine eligibility. These questions will assess the length of time since the suspected mTBI incident, general health, medications, and contraindications for MRI scanning or light therapy, and the presence of sleep disruption. Eligibility will require an mTBI within the past 18 months, with either no loss of consciousness (LOC) or LOC lasting less than 30 minutes and (if scores are available) a Glasgow Coma Scale of 13-15. Furthermore, half of the subjects assigned to each group will be required to show evidence of sleep onset insomnia or delayed sleep phase, as identified through screening and questionnaires. Additionally, participants engaging in shift-work, night work, or those with substantially desynchronized work-sleep schedules (i.e., sleeping later than 10:00 a.m. more than once a week) will be excluded. Individuals meeting basic eligibility requirements will be instructed how to provide physician/medical/professional verification of their head injury and will be scheduled for an initial assessment session.

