whether to use the light immediately upon arising, or after morning hygiene, meals, drive, etc., but will still ensure that all treatment occur in the morning hours. The instrument is equipped with a timer to ensure 30 minutes of exposure. Appropriate use will involve placing the light device at a distance between 12-24 inches, offset from center to reduce glare. Participants will be instructed not to look directly at the light source, but to allow the light to enter from their peripheral vision. Each morning, within 2 hours of arising from sleep, participants will 1) document the time, indicate sleepiness using the Stanford Sleepiness Scale (SSS), activate the light device, and document the sleep and wake times from the previous day. At the completion of the light period, participants will again indicate sleepiness using the SSS. To further monitor compliance, the wrist actigraph will also include a light monitor. Participants will be instructed to ensure that the light sensor of the actigraph is exposed to the light source for the full 30-minute duration in order to verify compliance. This will permit cross-verification that subjects have in fact used the blue wavelength light at the specified times (and will allow co-variation for additional light effects in statistical analyses). MBLT exposure will be conducted daily for 6-weeks for all participants. Participants will also be contacted weekly by phone to ensure compliance, answer questions, and collect a weekly Epworth Sleepiness Scale.

Half of the participants will be randomly assigned to the morning MBLT or a sham placebo light treatment (SPLT). Participants in the MBLT group will be administered blue light therapy using the standard goLITE BLU device, whereas participants in the SPLT group will be given identical appearing goLITE devices where the standard bright blue-wavelength LEDs have been replaced with amber LEDs. The goLITE BLU has been shown to have a narrow bandwidth, peaking at  $\lambda = 469$  nm, at 214 Lux, and panel irradiance  $\text{mW/cm}^2 = 1.23$  at 20 cm. A similar appearing amber LED system (goLITE AMBER) will be employed for the SPLT devices, but will peak at  $\lambda = 566$  nm, at 180 Lux, and total irradiance  $(\text{mW/cm}^2) = 0.58$ .

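### The main arm sets a sleep-complaint quota for each condition, but the allocation described (plain random assignment) does not secure it

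*Combined protocol and SAP*

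**What the plan says.** The quota appears in three places in Section 3, not in the same form.

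- **5) Study Population, Main Study Arm:** "at least half of the participants recruited for each condition will be required to have complaints consistent with sleep onset insomnia" or delayed sleep phase disorder. The Insomnia Severity Index (ISI) is named as the measure of insomnia, without a cut-off.
- **5) Study Population, Inclusion criteria:** "At least half of subjects must have evidence of sleep onset insomnia or delayed sleep phase disorder". This applies to the sample as a whole.
- **7) Procedures, Telephone Screening:** "half of the subjects assigned to each group will be required to show evidence of sleep onset insomnia or delayed sleep phase". This is again by group, but without 'at least'. The same sentence says how a person's status is to be established: "as identified through screening and questionnaires".

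The main-arm allocation is described twice. The Background says "participants will be randomly assigned to receive 30 minutes of morning blue light therapy (MBLT") or sham, and Six-Week Light Exposure Treatment says "Half of the participants will be randomly assigned to the morning MBLT or a sham placebo light treatment (SPLT"). Neither mentions strata, blocks or minimisation. The one block scheme in the document, in the Lay Summary, belongs to the healthy control arm and balances sex.

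The ISI is not among the instruments listed under Initial Assessment or under Personality and Psychodiagnostic Assessment. Section 4 lists a Phone Screening Form, a Questionnaire Task List, a separate protocol and a treatment schema. None of these was supplied.

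**The concern.** The three statements are compatible, but meeting the overall criterion does not ensure the rule for each condition. Staff could follow the inclusion criteria and the allocation text exactly and still break the rule in Study Population and Telephone Screening.

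The factor matters. The intervention is meant to work through sleep, and comparing sleep and mood between arms is Objective 1. With 30 planned completers, a difference of a few people in who had the target complaint at entry makes a between-arm difference in sleep or symptoms harder to read. The plan itself judged the factor important enough for a quota in each condition, but gives neither a mechanism nor a cut-off for who counts.

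**Working it through.** The plan states no figure on this point, so there is nothing to reproduce. The question is how often plain random allocation breaks the quota.

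**Inputs**
- 40 enrolled (Study Population, Main Study Arm). I take 20 per arm, since the treatment section assigns half to each.
- Quota: at least half of each arm, so at least 10 of 20.
- K, the number of the 40 who qualify. The plan gives only the floor of one half, so I let K run upward from 20.

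**Step 1: fixed 20/20 split, not stratified.** The number qualifying in one arm, a, is hypergeometric. Both arms meet the quota when a ≥ 10 and K − a ≥ 10:

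P(met) = Σ C(20, a) · C(20, K − a) / C(40, K).

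At K = 20 only a = 10 works: C(20,10)² / C(40,20) = 184,756² / 137,846,528,820 = 0.248, so P(missed) = 0.752. Of this, 2 · C(20,9)² / C(40,20) = 2 × 167,960² / 137,846,528,820 = 0.409 is an arm just one person short. The remaining 0.343 is two or more short.

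The last column replaces the fixed split with independent coin flips, counting a miss when either arm's qualifying share is below one half.

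| K qualifying of 40 | Missed, fixed 20/20 | Missed, coin flips |
|---|---|---|
| 20 | 75.2% | 87.5% |
| 22 | 34.1% | 43.0% |
| 24 | 10.5% | 15.4% |
| 26 | 1.9% | 3.9% |
| 28 | 0.1% | 0.6% |

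**Step 2: averaging over K.** Suppose a proportion p of eligible people qualify and the overall criterion is enforced by closing the non-qualifying group at 20. Then K = max(20, Binomial(40, p)), and P(missed) is the Step 1 value (fixed split) averaged over that distribution. Both p and the closing rule are my assumptions. The Background cites insomnia in 40 to 65% of mTBI patients, a related but not identical condition.

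| p | 40% | 50% | 60% | 65% | 70% | 80% |
|---|---|---|---|---|---|---|
| P(missed) | 72.5% | 54.6% | 22.0% | 9.9% | 3.3% | 0.1% |

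**Step 3: stratified allocation.** Let the first 20 slots of each stratum split 10/10, and close the non-qualifying stratum at 20. With K ≥ 20, all of the first 20 qualifying slots are used, so each arm has at least 10 qualifying. With 40 − K ≤ 20, each arm has at most 10 non-qualifying. Every arm is therefore at least half qualifying, for any K from 20 to 40. Simulating 5,000 lists per K with blocks of 4, 4, 6 and 6 in random order gave no misses; the largest between-arm difference in qualifying share was 15 percentage points.

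The 10/10 constraint matters. Freely varying blocks of 4 or 6 without it still miss in 36% of lists at K = 20 and 2% at K = 21.

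**The case against.** The strongest reply is that the rule is already stated at allocation level: Telephone Screening speaks of subjects assigned to each group, so allocation that ignored the phenotype would not comply. On that view only the implementation is missing, and it may sit in attachments not supplied. This stands as a limit on what can be concluded. The supplied text nevertheless contains no mechanism, and it describes a restricted scheme for the other arm.

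Second, the 75% is a worst case, and over half of it is a 9-versus-11 split. The Background describes participants "who complain of sleep disturbance, will undergo an initial psychological assessment", which suggests an enriched sample, and the risk is 3% or less once 70% or more qualify. This also stands, so the range should be read rather than its top. But sleep disturbance is broader than the quota condition, and if everyone qualified the quota would be redundant.

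Third, the consequence is modest: randomised inference stays valid, and no analysis in the Biostatistical Analysis section uses the quota. I agree, and do not claim bias.

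Fourth, blocking makes assignments easier to guess, because in the sham devices "the standard bright blue-wavelength LEDs have been replaced with amber LEDs" and the colour is visible. That is a real cost, given below. Simple fixed blocks of 4 would also secure the quota, with smaller imbalances (at most 10 points in share and 4 in arm size in simulation) but slightly higher predictability. The block sizes proposed here are one example.

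**Conclusion.** The concern holds. On the supplied text, the quota for each condition is not secured, and following the plan as written can break it. With 20 per arm, the probability runs from 75% when exactly half qualify down to 0.1% when 28 of 40 do. Across the cited 40 to 65% insomnia range it is about 72% to 10%, if that range applies to those screened and the non-qualifying group is closed at 20.

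The true share is unknown, and the unseen attachments could supply a mechanism, a cut-off or the timing of the ISI. A miss would be chance imbalance and would not invalidate the comparison. This should be fixed, because the plan already treats the factor as essential and intends to classify it at screening. The guarantee in Step 3 assumes that 40 are allocated with at least 20 qualifying. It covers those allocated, as the plan's rule does, not those who complete.

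**What to change.** 1. Align the three statements: by condition or overall, and half or at least half.
2. Define the sleep phenotype as yes or no before allocation, with one stated instrument and cut-off, and say when the ISI is given.
3. State the main-arm method: concealed 1:1 allocation stratified by that phenotype, in permuted blocks of randomly ordered varying size (for example 4, 4, 6, 6) that split the first 20 slots of each stratum 10/10, with the non-qualifying stratum closed at 20 of 40. If an unsupplied document already states a method, cite it.
4. Compare arms by ANCOVA on the post-treatment score, adjusting for its baseline value and the stratum, so that the analysis reflects the design.

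**Cost.** The change needs a stratified list held by someone who does not enrol, a few sentences of text, and one short questionnaire if the ISI is not already given. Recruitment may slow once the non-qualifying stratum closes. Always guessing the arm that is behind would be right 68 to 69% of the time, against 59% under a plain 20/20 split and 70 to 71% with fixed blocks of 4; concealment and an undisclosed block order reduce the harm. In the worst case the arms are 23 and 17. With 30 completers the two covariates leave 30 − 4 = 26 residual degrees of freedom instead of 30 − 2 = 28, moving the critical t from 2.048 to 2.056.
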